
 To evaluate the effects of SAR440340 compared with placebo, on patient reported symptoms and quality of life as documented by e-Diary and utilizing Exacerbations of Chronic Obstructive Pulmonary Disease Tool (EXACT), St. George's Respiratory Questionnaire (SGRQ) and Euroqol-5Dimension (EQ 5D) questionnaire 
 in all patients treated with SAR440340/placebo in subpopulations with high blood eosinophil level (≥ 250 /mm³) and low blood eosinophil level (<250 /mm³) 	
 Change from baseline in the EXACT scores at Week 24 Change from baseline in the SGRQ scores at Week 24 Change from baseline in the EQ-5D scores at Week 24

 To evaluate the pharmacokinetic (PK) profile of SAR440340 in serum 	
 Serum functional SAR440340 concentrations

 To evaluate the effects of SAR440340 Antidrug antibodies (ADA) 	
 Antidrug antibodies (ADA) against SAR440340

 To evaluate the effects of SAR440340 compared with placebo, on FEV1, AECOPD, and other relevant endpoints 
 in subpopulations with high blood eosinophil level (≥ 250 /mm³) and low blood eosinophil level (<250 /mm³) in subpopulations according to use/no use of ICS 	
 Change from baseline to Week 24 in FEV1 (pre-bronchodilator and post-bronchodilator) Rate of moderate-to-severe AECOPD

Objectives	Endpoints
with bronchodilators as background therapy, fibrinogen levels, and smoking status.	

 To evaluate the effects of pharmacogenomics on SAR440340 	
 Future Assessment of DNA or RNA samples for the pharmacogenomics sub study to identify genomic associations with clinical or biomarker response, other clinical outcome measures and possible AEs

 To evaluate the effects of SAR440340 compared with placebo on other respiratory assessments (expanded AECOPD endpoint) 	
 Change from baseline to Week 16-24 in FVC (% predicted and absolute values in mL). Time to the first moderate and severe exacerbations or time to study drug discontinuation (after Week 4) due to lack of efficacy, based on the investigator's judgement (expanded AECOPD endpoint)

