8.1 EFFICACY ASSESSMENTS

8.1.1 Disease-specific efficacy measures

8.1.1.1 COPD exacerbation

Severity of COPD exacerbations as defined by the protocol

“Moderate exacerbations” are recorded by the Investigator and defined as AECOPD that require either systemic corticosteroids (such as intramuscular, intravenous or oral) and/or antibiotics. “Severe exacerbations” are recorded by the Investigator and defined as AECOPD requiring hospitalization, emergency medical care visit or resulting in death.

All other exacerbations will be classified as “mild”.

Clinical symptoms of exacerbations of COPD

In addition to the protocol-defined exacerbations of COPD listed above, clinical signs and symptoms of exacerbations of COPD will be captured in the eCRF (including, but not limited to increase in dyspnea, increase in wheezing, increase in cough, increase in sputum volume and/or increase in sputum purulence).

Management of exacerbations of COPD

Exacerbations of COPD should be treated as deemed necessary by the investigator. After successful management of an acute exacerbation of COPD (e.g. with oral corticosteroids and/or antibiotics), all efforts should be made to resume the initial background COPD treatment regimen if in the investigator's opinion this is medically acceptable. After 1 severe or 2 moderate exacerbations of COPD, dose adjustments in background therapy will be permitted for symptom control and as needed for the remainder of the trial period.

Protocol defined COPD exacerbation events are collected as efficacy endpoints via the exacerbation eCRF page. These events should not be reported as AEs unless they fulfill a seriousness criterion. Any course of systemic steroids/antibiotics started <7 days of finishing a previous course should be considered as treatment for a single exacerbation.

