8.3.7 Disease-related events and/or disease-related outcomes not qualifying as AEs or SAEs

In this study, some AEs are considered related to the underlying condition and thus will not be considered unexpected. Specifically, for patients with COPD worsening of underlying condition is not considered an AE unless it meets serious criteria as defined in Appendix 3 ([Section 10.3](#)).

Any other AE not listed as an expected event in the IB or in this protocol will be considered unexpected.

8.3.8 Guidelines for reporting product complaints / medical device incidents (including malfunctions)

Any defect in the IMP/NIMP/device must be reported as soon as possible by the Investigator to the monitoring team that will complete a product complaint form within required timelines.

Appropriate information (eg, samples, labels or documents like pictures or photocopies) related to product identification and to the potential deficiencies may need to be gathered. The Investigator will assess whether or not the quality issue has to be reported together with an AE or SAE.

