9.2 SAMPLE SIZE DETERMINATION

To assess the power of the primary efficacy endpoint the annualized rate of moderate-to-severe AECOPD, we assume

- Average of 1.0 to 1.5 AECOPD per year in the placebo group of this study population enriched for severity and high risk of AECOPD.
- The number of AECOPD follows a negative binomial distribution with dispersion parameter 1.5 (8) for all the groups.
- A Wald-test is used to test whether the risk ratio is 1 with 2-sided 5% significance level.
- Patients will be treated with a minimum of 24 weeks and a maximum of 52 weeks depending on their study entry times. The monthly cumulative patient accruals are assumed to be 1, 5, 10, 25, 50, 90, 150, 210, 270, 335 and 340 for an eleven (11)-month accrual period.
- Cumulatively, 9%, 15% and 20% of patients drop out of the study due to discontinuation or other reasons by 12, 24 and 52 weeks after study entry.
- Patients are randomized to the treatment group and the placebo group with a 1:1 ratio.

With these assumptions and 170 patients per group (340 patients in total), the study will yield 81.6% to 88.8% powers with risk reduction equal to 45% and the placebo rate ranging from 1.0 to 1.5 per year. To obtain at least 80% power, the minimum risk reduction is from 44.2% to 40.6%. The minimum detectable risk reduction (i.e. with 50% power) is from 32.7% to 30.0%. See the table below for more details.

Table 12 - Power calculation for various event rates in the placebo group

Placebo rate	Power for certain Risk Reduction (RR)			Minimum RR for certain power	
	RR=40%	RR=45%	RR=50%	Power=80%	Power=50%
1.0	69.9%	81.6%	90.3%	44.2%	32.7%
1.2	74.1%	85.2%	92.9%	42.5%	31.4%
1.5	78.5%	88.8%	95.2%	40.6%	30.0%

RR: risk reduction

Based on the accrual and drop-out assumptions, the mean exposure time is 35.5 (±12.8) weeks. Since we use variable follow-up times for patients entering at different times, the power will depend on the actual accrual rates and the drop-out rates. We will closely monitor these rates. If the accrual rates are significantly lower than planned and/or the drop-out rates are higher than expected, the minimum treatment period may be extended to achieve the desired amount of total exposure. The maximum treatment period of 52 weeks will not be changed.

To assess the key secondary efficacy endpoint the change from baseline to Week 24 in post-bronchodilator FEV1, we assume that:

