- Exacerbation of a chronic or intermittent pre-existing condition including either an increase in frequency and/or intensity of the condition
- New conditions detected or diagnosed after IMP administration even though it may have been present before the start of the study
- Signs, symptoms, or the clinical sequelae of a suspected drug-drug interaction
- Signs, symptoms, or the clinical sequelae of a suspected overdose of either IMP or a concomitant medication
- "Lack of efficacy" or "failure of expected pharmacological action" per se will not be reported as an AE or SAE. Such instances will be captured in the efficacy assessments. However, the signs, symptoms, and/or clinical sequelae resulting from lack of efficacy will be reported as AE or SAE if they fulfil the definition of an AE or SAE
- The signs, symptoms, and/or clinical sequelae resulting from lack of efficacy will be reported as AE or SAE if they fulfil the definition of an AE or SAE. Also, "lack of efficacy" or "failure of expected pharmacological action" also constitutes an AE or SAE.

Events **NOT** meeting the AE definition

- Any clinically significant abnormal laboratory findings or other abnormal safety assessments which are associated with the underlying disease, unless judged by the Investigator to be more severe than expected for the participant's condition.
- The disease/disorder being studied or expected progression, signs, or symptoms of the disease/disorder being studied, unless more severe than expected for the participant's condition (see [Section 8.3.7](#)).
- Medical or surgical procedure (eg, endoscopy, appendectomy): the condition that leads to the procedure is the AE
- Situations in which an untoward medical occurrence did not occur (social and/or convenience admission to a hospital)
- Anticipated day-to-day fluctuations of pre-existing disease(s) or condition(s) present or detected at the start of the study that do not worsen

DEFINITION OF SAE

If an event is not an AE per definition above, then it cannot be an SAE even if serious conditions are met (eg, hospitalization for signs/symptoms of the disease under study, death due to progression of disease).

A SAE is defined as any untoward medical occurrence that, at any dose:

a) Results in death

b) Is life-threatening

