2.4.5.1 Analyses of adverse events

Generalities

The primary focus of adverse event reporting will be on TEAEs. Pre-treatment and post-treatment adverse events will be described separately.

If an adverse event date/time of onset (occurrence, worsening, or becoming serious) is incomplete, an imputation algorithm will be used to classify the adverse event as pre-treatment, treatment-emergent, or post-treatment. The algorithm for imputing date/time of onset will be conservative and will classify an adverse event as treatment emergent unless there is definitive information to determine it is pre-treatment or post-treatment. Details on classification of adverse events with missing or partial onset dates are provided in [Section 2.5.3](#).

Adverse event incidence tables will present the number (n) and percentage (%) of patients experiencing an event by treatment group. Multiple occurrences of the same event in the same patient will be counted only once in the tables within a treatment phase. The denominator for computation of percentages is the safety population within each treatment group. Sorting will be based on results for the SAR440340 group by the following orders:

- Tables presented by SOC: sorted by internationally agreed SOC order
- Tables presented by PT: sorted by decreasing frequency of PT
- Tables presented by SOC and PT: sorted by internationally agreed SOC order and decreasing frequency of PT within SOC

Analysis of all TEAEs

The following TEAE summaries will be generated for the safety population.

- Overview of TEAE, summarizing number (%) of patients with any
 - TEAE
 - Severe TEAE

- Serious TEAE
- TEAE leading to death
- TEAE leading to permanent treatment discontinuation
- All TEAEs by primary SOC
- All TEAEs by PT
- All TEAEs by primary SOC and PT
- All TEAEs related to SAR440340 or matching placebo by primary SOC and PT
- All TEAEs by maximal severity, presented by primary SOC and PT
- Listing of all TEAEs

Analysis of all treatment emergent SAEs

- All treatment-emergent SAEs by primary SOC and PT
- All treatment-emergent SAEs by PT
- All treatment-emergent SAEs related to SAR440340 or matching placebo by primary SOC and PT
- Listing of all treatment-emergent SAEs

Analysis of all TEAEs leading to permanent treatment discontinuation

- All TEAEs leading to permanent treatment discontinuation by primary SOC and PT
- All TEAEs leading to permanent treatment discontinuation by PT

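### Protocol Appendix 3 says both that lack of efficacy is not an adverse event and that it is one, so the safety tables can mix two AE definitions, with a limited tilt in the drug's favour if the drug works

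*Protocol*

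**What the plan says.** Protocol Section 10.3 lists events that meet the AE definition. One bullet says that lack of efficacy, or failure of the expected pharmacological action, "per se will not be reported as an AE or SAE" and adds: "Such instances will be captured in the efficacy assessments". It ends by saying that resulting signs, symptoms or sequelae are reported if they meet the AE or SAE definition themselves. The next bullet repeats that last sentence and then says that lack of efficacy "also constitutes an AE or SAE".

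Two other sections deal with neighbouring events. Protocol 8.1.1.1 says of protocol-defined exacerbations: "These events should not be reported as AEs unless they fulfill a seriousness criterion". Protocol 8.3.7 says that for COPD patients "worsening of underlying condition is not considered an AE unless it meets serious criteria as defined in Appendix 3".

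Two outputs could be affected. SAP 2.4.5.1 makes TEAEs the main focus of safety reporting and includes a table of "All TEAEs leading to permanent treatment discontinuation by primary SOC and PT". Protocol Table 1 has a tertiary expanded AECOPD endpoint with the component "time to study drug discontinuation (after Week 4) due to lack of efficacy", which rests on the investigator's judgement.

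**The concern.** A site cannot follow both bullets. Some will enter lack of efficacy as an AE and others will not, and the SAP has no rule to separate such records. The TEAE tables would then combine two definitions, in proportions set by how each site reads the appendix.

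Safety and tolerability is a stated secondary objective, judged by comparing TEAEs and SAEs between the arms. In a placebo-controlled trial the error would have a direction. If the drug reduces exacerbations, efficacy failure is more common on placebo, so these records add more AEs there and can dilute a true AE excess on the drug. The AE definition also decides what can be an SAE, and SAEs are reported within 24 hours (Protocol 8.3.2). The bullets therefore disagree on reporting duties as well as on tables.

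**Working it through.** **Step 1. Set the rules side by side.**

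| Place | Subject | Instruction |
|---|---|---|
| 10.3, one bullet | lack of efficacy as such | not an AE; captured as efficacy |
| 10.3, next bullet | lack of efficacy as such | is an AE or SAE |
| 8.1.1.1 | protocol-defined exacerbation | not an AE unless serious |
| 8.3.7 | worsening of COPD | not an AE unless serious |

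The first two rows have the same subject and opposite instructions. The last two do not mention lack of efficacy as such, so they do not settle the conflict, but they do limit what it can affect.

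**Step 2. Find what can leak.** Non-serious exacerbations and COPD worsening stay out under 8.1.1.1 and 8.3.7. Serious ones are reported under those sections whichever bullet a site follows, so they are not extra records. What remains is lack of efficacy entered as an AE term of its own, and treatment stops attributed to such an AE.

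**Step 3. Illustrate the size.** The documents give no figure for this, so I used the planning model as a scale.

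Inputs from Protocol 9.2: 170 patients per group, with allocation as stated ("Patients are randomized to the treatment group and the placebo group with a 1:1 ratio"); placebo rate 1.0 to 1.5 per year; negative binomial dispersion k = 1.5; 45% reduction; the listed monthly accrual; cumulative drop-out of 9%, 15% and 20% by Weeks 12, 24 and 52. My assumptions: uniform entry within each month and linear drop-out between the stated weeks.

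Check against the plan's own figures:
- Simulated exposure t has mean 35.5 weeks and SD 12.8, as stated.
- Information per arm: I(λ) = 170 × mean[λt / (1 + kλt)], with t in years.
- Power = Φ(−ln(1 − RR)/SE − 1.96), with SE² = 1/I(placebo) + 1/I(active).
- For a 45% reduction this gives 81.6% at rate 1.0 and 88.8% at 1.5, matching Protocol Table 12. All nine power cells agree within 0.1 point.

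Probability that a patient has at least one moderate-to-severe exacerbation: P = 1 − mean[(1 + kλt)^(−1/k)].

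| Placebo rate | Placebo | Active | Gap, patients per 170 |
|---|---|---|---|
| 1.0 | 36.0% (61.1 patients) | 24.9% (42.3) | 18.8 |
| 1.2 | 39.6% (67.3) | 28.1% (47.7) | 19.6 |
| 1.5 | 44.1% (75.0) | 32.2% (54.8) | 20.3 |

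Gaps are taken before rounding. The share of these patients who would get a lack-of-efficacy AE record is not in the documents. Taking the same share f in both arms, excess on placebo = f × gap:
- f = 10%: 1.9 to 2.0 patients
- f = 25%: 4.7 to 5.1 patients
- f = 50%: 9.4 to 10.1 patients

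So the placebo excess is about 2 to 10 patients per 170, or 1.2% to 5.9% of an arm (2/170 and 10/170).

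**The case against.** The strongest reply is that the stakes are small. SAP 2.4.5 makes the safety analysis essentially descriptive, with no systematic testing. SAP 2.4.5.1 tabulates by preferred term and lists every TEAE, so a lack-of-efficacy term could be seen and set aside. Exacerbations have their own eCRF page (Protocol 8.1.1.1), so the primary endpoint does not depend on either bullet. All of this stands, and it limits the consequence. It does not remove the contradiction, because no section tells a site which bullet to apply.

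Three stronger readings are tempting, and the documents do not support them.

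- A reader might treat every exacerbation as an extra AE: 170 × 35.5/52 = 116 patient-years per arm, so 116 to 174 events on placebo against 64 to 96 on drug, an excess of 52 to 78. That assumes what 8.1.1.1 and 8.3.7 forbid for non-serious events, and it counts serious ones that are reported anyway. It also uses the wrong unit: SAP 2.4.5.1 counts patients, with repeats of an event in one patient counted once.
- A reader might size the effect on AE discontinuations from the 15% to 20% drop-out in Protocol 9.2. That figure is drop-out from the study, which the protocol separates from stopping IMP. It covers both arms together, and the documents do not say what share stops for lack of efficacy.
- A reader might infer that the expanded AECOPD endpoint loses events. That is possible but not shown. The component rests on the investigator's judgement, SAP 2.2 summarises the main reason for permanent discontinuation separately, and a patient with an earlier moderate or severe exacerbation already has the event.

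**Conclusion.** The contradiction is literal and needs correcting. Its consequence is a mixed AE definition in the TEAE and AE-discontinuation tables, with a tilt in the drug's favour only if the drug works; with no effect, the tables would be inconsistent but not biased in expectation.

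The figure of about 2 to 10 placebo patients per 170 is an illustration, not a forecast. It rests on the planning rates, the 45% reduction, an assumed recording share of 10% to 50% equal in both arms, and the use of patients with an exacerbation as a stand-in for patients judged to lack efficacy. If few sites apply the second bullet, the excess could be close to zero. The point deserves action because the correction is cheap, not because a large distortion has been shown.

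**What to change.** 1. Delete the second bullet. The sentence it opens with already closes the preceding bullet, so only the contradictory clause is lost.
2. Add a cross-reference from that place to Sections 8.1.1.1 and 8.3.7.
3. Reconcile the rest of Section 10.3 with those two sections, because the deletion alone does not do so. The appendix still lists exacerbation of a pre-existing chronic condition as an AE. It also says that an event outside the AE definition cannot be an SAE, and gives hospitalization for the disease under study as an example. Sections 8.1.1.1 and 8.3.7 treat non-serious exacerbations as outside AE reporting and serious ones as inside it.
4. State in the CRF completion guide that stopping IMP for lack of efficacy is recorded under that reason and not as an AE.
5. If lack-of-efficacy AE records already exist, say in the SAP how they are shown.

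The cost is a short wording change in a protocol amendment, a line in the CRF guide and, if needed, a sentence in the SAP. No new data are required.

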8.3.2 Time period and frequency for collecting AE and SAE information

All AEs and SAEs will be collected from the signing of the ICF up to the end of study visit at the time points specified in the SoA ([Section 1.3](#)), or up to recovery or stabilization of any AE to be followed-up as specified in this protocol, whichever comes last.

All SAEs and AESI will be recorded and reported to the Sponsor or designee within 24 hours, as indicated in Appendix 3 ([Section 10.3](#)). The Investigator will submit any updated SAE and AESI data to the Sponsor within 24 hours of it being available.

Investigators are not obligated to actively seek AE or SAE after conclusion of the study participation. However, if the Investigator learns of any SAE, including a death, at any time after a participant has been discharged from the study, and he/she considers the event to be reasonably related to the IMP or study participation, the Investigator must promptly notify the Sponsor.

The method of recording, evaluating, and assessing causality of AE and SAE and the procedures for completing and transmitting SAE reports are provided in Appendix 3 ([Section 10.3](#)).

Adverse event (SAE and AESI) reporting is summarized in [Table 7](#).

Table 7 – Adverse event reporting

Adverse event/laboratory abnormality	Reporting timeframe
Serious adverse event	Within 24 hours
Pregnancy	Within 24 hours
Overdose	Symptomatic Asymptomatic
	Routine
ALT elevation	
	ALT >3 x ULN and associated with total bilirubin >2 x ULN
	Within 24 hours
	ALT >5 ULN if baseline ALT is ≤2 ULN
	Within 24 hours
	ALT >8 ULN if baseline ALT is >2 ULN
	Within 24 hours
Anaphylactic or systemic allergic reactions that require treatment.	Within 24 hours

Adverse event/laboratory abnormality	Reporting timeframe
Severe injection site reactions that last longer than 24 hours.	Within 24 hours
Infections as defined in Table 6	Within 24 hours
Malignancy	Within 24 hours

ALT: alanine aminotransaminase; ULN: upper limit of normal.

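### Appendix 3 offers disease-related hospitalisation and death as events that cannot be SAEs, while Protocol 8.1.1.1 and 8.3.7 make a serious COPD exacerbation reportable; nothing says which prevails

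*Protocol*

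**What the plan says.** **Section 8.1.1.1 (COPD exacerbation).** Protocol-defined exacerbations go on their own eCRF page. "These events should not be reported as AEs unless they fulfill a seriousness criterion".

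**Section 8.3.7 (disease-related events).** It states that "for patients with COPD worsening of underlying condition is not considered an AE unless it meets serious criteria", and takes those criteria from Appendix 3.

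**Section 10.3 (Appendix 3), events not meeting the AE definition.** The excluded items include "symptoms of the disease/disorder being studied, unless more severe than expected" for that participant. The bullet refers the reader to 8.3.7.

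**Section 10.3, definition of SAE.** It opens with "If an event is not an AE per definition above, then it cannot be an SAE even if serious conditions are met". The bracketed examples are "hospitalization for signs/symptoms of the disease under study, death due to progression of disease".

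**Section 10.3, lack of efficacy.** One bullet says lack of efficacy "per se will not be reported as an AE or SAE". The next says it "also constitutes an AE or SAE". Both agree that resulting signs, symptoms or sequelae are reported if they meet the definition.

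**Section 8.3.2.** "All SAEs and AESI will be recorded and reported to the Sponsor or designee within 24 hours".

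**The concern.** Sections 8.1.1.1 and 8.3.7 ask whether the event is serious. The Appendix 3 exclusion asks whether it is worse than expected for that patient. These are different tests, and Appendix 3 itself warns, under assessment of intensity, against confusing severity with seriousness.

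Exacerbation is the primary endpoint event, and the protocol's severe category includes hospitalisation and death, so this is not a rare corner case. A site that relies on the Appendix 3 example would not send the expedited report. The event would also be absent from the treatment-emergent SAE tables (SAP 2.4.5.1) and from TEAEs leading to death (SAP 2.4.5.2), which is built from the AE page. TEAEs and SAEs are a named secondary endpoint in Protocol Table 1. If sites differ in their reading, the SAE tables mix two conventions.

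Three things are untouched: the primary endpoint, exacerbation capture on its own eCRF page, and the count of deaths by study period in SAP 2.4.5.2.

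**Working it through.** **1. One event under each rule.** Take an exacerbation that leads to inpatient admission and is no more severe than expected for that patient. Inpatient hospitalisation is seriousness criterion (c) in Appendix 3; death is criterion (a).

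| Text | Test applied | Result |
|---|---|---|
| Protocol 8.1.1.1 | Is a seriousness criterion met? Yes | AE, hence SAE |
| Protocol 8.3.7 | Are the serious criteria met? Yes | AE, hence SAE |
| Appendix 3, non-AE list | More severe than expected? No | Not an AE |
| Appendix 3, SAE definition and examples | A non-AE cannot be an SAE | Not an SAE |

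The classifications are opposite. Appendix 3 is also not uniform within itself, because its list of events that do meet the AE definition includes worsening of a pre-existing chronic condition.

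**2. Does any text settle it?** The non-AE bullet points to 8.3.7, and 8.3.7 points back to Appendix 3 for the serious criteria, so the references are circular. The SAP safety sections (2.1.4 and 2.4.5) contain no rule for exacerbations.

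**3. Lack of efficacy.** The two adjacent bullets assert a statement and its negation, and no reading makes both true.

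**4. Illustrative size, placebo arm.** The contradiction does not depend on this; it only shows how many events could turn on the reading.

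- Inputs from Protocol 9.2: 170 patients per arm, mean exposure 35.5 weeks, placebo rate 1.0 to 1.5 moderate-or-severe exacerbations per year.
- Patient-years = patients x weeks / 52 = 170 x 35.5 / 52 = 116.1.
- Expected exacerbations = 116.1 x 1.0 to 116.1 x 1.5 = 116.1 to 174.1.
- Share meeting a seriousness criterion: not given. It cannot be taken from the severe category, because that category also counts emergency visits, which need not meet a seriousness criterion. Assumed range: 5% to 30%.
- Events at issue = 116.1 x 0.05 to 174.1 x 0.30 = 5.8 to 52.2, about 6 to 52.

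The TEAE period also includes the residual treatment epoch (SAP 2.1.4), from day 15 to day 154 after the last dose: (154 - 14) / 7 = 20 weeks. If nobody is lost in follow-up and the rate is unchanged:

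- Patient-years = 170 x (35.5 + 20) / 52 = 181.4.
- Events at issue = 181.4 x 1.0 x 0.05 to 181.4 x 1.5 x 0.30 = 9.1 to 81.6, about 9 to 82.

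**The case against.** The best defence is that Appendix 3 defers to 8.3.7. Its SAE bar is conditional on the event not being an AE, the disease bullet cites 8.3.7, and two COPD-specific sections agree. On that reading a serious exacerbation is an AE, so the bar never applies. A site would have to prefer a generic example to two specific instructions in order to under-report.

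This is a fair reading, and many sites may adopt it. It does not remove the conflict. If 8.3.7 governs, the hospitalisation example cannot apply to COPD, yet it stands in the SAE definition that 8.3.7 sends sites to consult.

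There are also partial safeguards. A serious infection, or one needing parenteral antimicrobials, is an AESI with 24-hour notification, and Protocol 2.2.1 says exacerbations are mostly infective. The DMC reviews unblinded data on an ongoing basis, and the safety analysis is descriptive. These narrow the consequence, but the AESI route works only if the infection itself is recorded as an adverse event, and neither safeguard puts an omitted exacerbation into the SAE tables.

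The objection to the size is partly right. The 5% to 30% share is an assumption, and the figures cover the placebo arm only. Even if every site followed Appendix 3, exacerbations judged worse than expected would remain SAEs, so the real swing would be smaller than the figure shown. For the placebo arm, under the stated assumptions, it remains an upper bound.

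The lack-of-efficacy contradiction is a lesser, separate defect and adds little to the SAE point.

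**Conclusion.** The concern holds and should be fixed. The text conflict is certain. How often it would change a report is not, because nothing in the documents shows which reading sites would follow.

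The placebo-arm ranges above would be reached only if all sites followed one reading rather than the other, and they rest on the Protocol 9.2 planning assumptions and the assumed serious share.

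Under blinding the chance of omission should be similar in the two arms, so the main effects are an understated SAE count and missed expedited notifications, not a bias toward one arm. The number omitted would still follow each arm's exacerbation rate, so a true between-arm difference in SAE counts could look smaller than it is.

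**What to change.** Make Appendix 3, 8.1.1.1 and 8.3.7 state one rule. The smallest edit is to delete the bracketed example from the SAE definition and to put the same seriousness exception into the disease-under-study bullet, since two sections already use it. Keep only one of the two lack-of-efficacy bullets. Send sites a short note on the reconciled rule.

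Showing SAEs with and without exacerbation terms is optional, because SAP 2.4.5.1 already tabulates them by preferred term.

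The cost is a wording correction in the next amendment and the site note. Data collection and the planned analyses stay as they are.
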